### 2.2.2 Rationale for cMET mutation cohorts

cMET mutations leading to exon 14 deletion have been identified as an actionable target for cMET inhibition in NSCLC (Kong-Beltran et al 2006, Salgia 2017, Despcarpetries 2018). Based on the data available, the overlap between high cMET amplification (defined as FISH GCN  $\geq 6$ ) and cMET mutations, although possible, has not been elucidated yet (TCGA web portal 2015, internal Novartis data) and no overlap between cMET mutation and either EGFR mutations or ALK translocation is expected (TCGA web portal 2015). Growing clinical data on the activity of cMET inhibitors in cMET-mutated NSCLC have been published showing promising efficacy, irrespective of the histology, making cMET mutations an attractive molecular target in advanced NSCLC (Frampton 2015, Jenkins 2015, Mendenhall 2015, Paik 2015, Waqar 2015, Liu 2015, Awad et al 2016, Jorge et al 2015, Lee et al 2015, Mahjoubi et al 2016, Drilon et al 2016, Drilon et al 2017, Felip et al 2018, Wolf et al 2018).

There is a growing body of clinical evidence that shows that cMET mutation, in particular, is a predictor of response to cMET inhibitors irrespective of the line of treatment (Frampton et al 2015, Schuler et al 2016, Drilon et al 2016, Awad et al 2017, Drilon et al 2017, Felip et al 2018, Wolf et al 2018).

Based on these emerging data, the activity of cMET inhibitors warrants further exploration also in cMET-mutated NSCLC.

### **2.2.3 Rationale for treatment-naïve cohort with cMET dysregulation**

Increasing data confirms that cMET dysregulations such as cMET exon 14 skipping mutations and high cMET amplification are emerging as independent molecular drivers and predictors of response to cMET inhibition in NSCLC patients, irrespective of the number of prior lines of therapy including some preliminary evidence in the treatment-naïve setting (Frampton 2015, Jenkins 2015, Mendenhall 2015, Paik 2015, Waqar 2015, Liu 2015, Schuler 2016, Drilon 2016, Felip et al 2018, Drilon et al 2017, Wolf et al 2018).

Promising activity with INC280 in cMET dysregulated (either cMET amplified or cMET exon 14 skipping mutated) advanced NSCLC has been observed in the phase I study [CINC280X2102] (Schuler 2016). In patients with cMET amplified (GCN  $\geq 6$ ) NSCLC a 47 % ORR and median PFS of 7.4 months was reported. While these promising results were obtained mainly in pretreated patients, three patients (who declined chemotherapy) were enrolled as treatment-naïve. Two of these patients harbored cMET exon 14 skipping mutation (one had concurrent cMET amplification). Both patients gained benefit from INC280 treatment (tumor shrinkage -53.3% and -48.5%) achieving confirmed and unconfirmed partial responses, respectively. This result was consistent with the overall benefit gained by the other two cMET mutated patients enrolled in the study (pretreated with 1 and 3 prior lines of systemic therapy, respectively), leading to an ORR of 75% in cMET mutated patients (3 out of 4 patients achieved confirmed and durable partial responses). Overall, INC280 was well tolerated in both treatment-naïve and pretreated NSCLC patients.

While the data are still preliminary, cMET exon 14 skipping mutations and/or high cMET gene amplification are emerging as independent tumor drivers and patients harboring such cMET dysregulations can benefit from treatment with cMET inhibitors such as INC280, irrespective of prior lines of therapy and including treatment-naïve patients with acceptable safety profile. This concept was successfully confirmed in the treatment-naïve advanced NSCLC setting with other targeted agents directed against established molecular drivers such as EGFR mutation, ALK and ROS1 translocation which showed greater efficacy when compared with platinum-doublet chemotherapy (Rosell 2012, Sequist 2013, Solomon 2014). These data also confirmed that the safety profile of such targeted agents does not differ in the treatment-naïve setting compared to the pretreated setting.

There is no cMET inhibitor currently approved for cMET dysregulated NSCLC and the activity of platinum-based chemotherapy in patients with treatment-naïve advanced NSCLC harboring cMET exon 14 skipping mutations and/or high level of cMET amplification (GCN  $\geq 10$ ) is unknown.

## 2.2.4 Rationale for additional Cohort 6 in pretreated NSCLC with cMET dysregulation

While enrollment in the pretreated cohorts with cMET amplification less than 10 GCN (Sub-cohort 1b, Cohort 2 and Cohort 3) was stopped following the preplanned interim analyses for futility, Sub-cohort 1a (GCN  $\geq 10$ ) and Cohort 4 (cMET mutations) passed the futility criteria and enrollment is continuing until completion for these 2 cohorts.

In expansion Cohort 6, approximately additional 30 patients with advanced NSCLC pretreated with one prior line of systemic therapy harboring either cMET amplification (GCN  $\geq 10$ ) or cMET mutations (irrespective of cMET GCN) will be enrolled after enrollment of the respective Sub-cohort 1a/Cohort 4 is completed.

The main purpose of this additional cohort is to generate supportive safety and efficacy data in this second line patient population (which currently accounts for the majority of patients enrolled in the respective Sub-cohort 1a and Cohort 4). Therefore Cohort 6 is considered representative of the overall targeted patient population of pretreated cMET high amplified and mutated NSCLC.

## 2.2.5 Rationale for additional Cohort 7 in treatment-naïve NSCLC with cMET mutation

In light of the promising data generated in cMET mutated NSCLC in treatment naive setting in Sub-cohort 5b (Wolf et al 2018 - see [Section 1.2.1.2.2](#)), the main purpose of Cohort 7 is to generate additional supportive safety and efficacy data in this is first line patient population, which currently accounts for the patients enrolled in Sub-cohort 5b of this study.

## 2.3 Rationale for dose and regimen selection

As of 28-Sep-2014, the cut-off date of the IB available at the time of preparation of the original protocol, a total of 203 patients have been treated with INC280 as a single agent with either the capsule formulation (N=192) or tablet formulation (N=11). Five DLTs were experienced with INC280 as a single agent with the capsule formulation and no DLTs were observed with the tablet formulation (see [Table 2-1](#)).

**Table 2-1 DLTs experienced with single agent INC280 as of 28-Sep-2014**

Study and Treatment	N	Dose Limiting Toxicities
Study CINC280X1101		
INC280 capsules:		
100 mg QD	3	None
200 mg QD	4	None
400 mg QD	3	None
500 mg QD	4	None
600 mg QD	4	None
800 mg QD	4	None
400 mg BID	4	None
600 mg BID	3	Grade 2 malaise and suicidal ideation
INC280 tablets:		
200 mg BID	3	None

Study and Treatment	N	Dose Limiting Toxicities
400 mg BID	3	None
Study CINC280X2101		
INC280 capsules:		
10 mg QD	3	None
20 mg QD	4	None
50 mg QD	6	Grade 3 AST and ALKP increase
70 mg QD	4	None
50 mg BID	3	None
150 mg QD	3	None
200 mg QD	4	None
300 mg QD	4	None
400 mg QD	6	None
200 mg BID	4	None
300 mg BID	4	None
Study CINC280X2102		
INC280 capsules:		
100 mg BID	4	None
200 mg BID	5	Grade 3 fatigue
250 mg BID	4	Grade 3 blood bilirubin increased
350 mg BID	3	None
450 mg BID	9	Grade 3 fatigue
600 mg BID escalation	8	None
600 mg BID expansion	53	None
INC280 tablets:		
400 mg BID	5	None

Based on the data from study [CINC280X2102], and the observation that exposure did not further increase from 600 mg to 800 mg QD dosing, the RP2D of INC280 monotherapy in adults (in capsules) is 600 mg BID. Single-agent INC280 is generally tolerable at this dose when given twice daily on a continuous dosing schedule, with most adverse events (AEs) being manageable and of grade 1 and grade 2 severity.

As of 28-Sep-2014 ([Investigator's Brochure edition 5.2] data cut-off date), preliminary PK data were available from 10 patients treated with the INC280 tablet formulation as single agent at 200 mg or 400 mg BID dose. Based on the limited data, mean Cmax at steady-state following administration of INC280 tablets at 400 mg BID was 41% higher than that following capsules administration at 600 mg BID. Considering the 67% variability (CV%) observed with the capsule formulation at 600 mg BID, tablets at 400 mg BID (CV% = 30%) provided exposures within the range of exposures observed with capsules at 600 mg BID (the RP2D in study [CINC280X2102]).

In study [CINC280X2101] (single agent capsules), dose-dependent inhibition of phospho-cMET was observed across 11 dose cohorts (10 mg QD up to 400 mg QD or 300 mg BID) and complete inhibition was observed at trough concentration on Day 15 at 200 mg BID single agent capsules. In addition, complete inhibition of tumor cMET phosphorylation in patients was observed at 450 mg BID single agent capsules in study [CINC280X2102] and at 400 mg BID capsules in combination with gefitinib in study [CINC280X2202]. Based on the observed 400 mg BID tablet exposure, which appears to be higher in mean level but within

the range of 600 mg BID capsule exposure, the 400 mg BID tablet dose and regimen is expected to provide high enough inhibition levels to be efficacious. For details, refer to [Section 1.2.1.2.4](#) and [Investigator's Brochure edition 5.2].

Based on the available tablet PK and safety data, the dosage of INC280 at 400 mg BID in tablet formulation was found to be tolerable in patients and has been declared as the RP2D and is being further evaluated in the ongoing INC280 studies.

## **2.4 Rationale for choice of combination drugs**

Not applicable.

## **2.5 Rationale for choice of comparators drugs**

Not applicable.

[figure not shown]
## **3 Objectives and endpoints**

Objectives and related endpoints are described in [Table 3-1](#) below.

**Table 3-1 Objectives and related endpoints**

Objective	Endpoint	Analysis
Primary		
To evaluate the antitumor activity of INC280, as measured by overall response rate (ORR) by Blinded Independent Review Committee (BIRC) assessment, by cohort/sub-cohort	ORR, proportion of patients with a best overall response defined as complete response or partial response (CR+PR) by BIRC assessment per RECIST 1.1	Refer to Section 10.4
Key secondary		
To evaluate duration of response (DOR) as assessed by BIRC, by cohort/sub-cohort	DOR, calculated as the time from the date of the first documented CR or PR by BIRC per RECIST 1.1 to the first documented progression or death due to any cause for patients with PR or CR	Refer to Section 10.5.1
Other secondary		
1. To evaluate ORR and DOR by investigator assessment, by cohort/sub-cohort	ORR (CR+PR) and DOR per RECIST 1.1 by investigator assessment	Refer to Section 10.5.2
2. To evaluate time to response (TTR), disease control rate (DCR) and progression-free survival (PFS) by investigator and by BIRC assessment, by cohort/sub-cohort	All calculated per RECIST 1.1, both by BIRC and investigator: 
 
• TTR, calculated as the time from first dose of INC280 to first documented response (CR+PR) for patients with PR or CR
 
• DCR, calculated as the proportion of patients with best overall response of CR, PR, or SD
 
• PFS, defined as time from first dose of INC280 to progression or death due to any cause
 
	Refer to Section 10.5.2
3. To evaluate overall survival (OS), by cohort/sub-cohort	OS, defined as time from first dose of INC280 to death due to any cause	Refer to Section 10.5.2
4. To evaluate INC280 safety profile as monotherapy in NSCLC patients with advanced/metastatic disease	Incidence of adverse events and serious adverse events, change in vital signs, laboratory results (hematology, blood chemistry, and urinalysis) and ECG.	Refer to Section 10.5.3
5. To characterize the pharmacokinetics of INC280 and metabolite CMN288	Plasma concentration-time profiles and pharmacokinetic parameters estimated by non-compartmental analysis or population PK modeling	Refer to Section 10.5.4

Objective	Endpoint	Analysis

## 4 Study design

### 4.1 Description of study design

This is a prospectively designed, multicenter, open-label, phase II study to evaluate the efficacy and safety of single-agent INC280 in patients with EGFR wt (for exon 19 deletions and exon 21 L858R substitution mutations), ALK-negative rearrangement, advanced (stage IIIB or IV) NSCLC harboring cMET amplification and/or mutations.

Approximately 456 male and female patients aged 18 or over will be enrolled in this study in 7 separate cohorts [138 in Cohort 1 (69 patients per each Sub-cohort 1a and 1b) and 69 patients in each Cohorts 2, 3, and 4; 54 patients in Cohort 5 (27 patients per each Sub-cohort 5a and 5b); approximately 30 patients in Cohort 6; approximately 27 in Cohort 7] depending on their cMET amplification and/or mutation status and prior treatment status. A Bayesian interim monitoring for Cohorts 1, 2, 3 and 4, based on pre-specified response criteria is used (see [Section 10.7](#)) for a decision on whether to continue enrollment or stop for futility in the respective cohort. Due to the promising data for the treatment naïve patients from [\[INC280X2102\]](#) study, drug tolerability as observed in the other cohorts, and the outcome of the futility interim analyses in Sub-cohort 1a and Cohort 4, as well as the small sample size of Sub-cohorts 5a and 5b, interim analyses for futility are not being implemented in the treatment naïve Sub-cohorts, Cohort 6 and Cohort 7.

For patients with NSCLC, EGFR mutation and ALK rearrangement status should have been assessed as part of the patients standard of care using a validated test as per the Molecular Testing Guideline for Selection of Lung Cancer Patients for EGFR and ALK Tyrosine Kinase Inhibitors from College of American Pathologists, International Association for the Study of Lung Cancer, and Association for Molecular Pathology ([Lindeman et al 2013](#)). The EGFR wt status (for exon 19 deletions and exon 21 L858R substitution mutations) must be documented in the patient source documents before patient can be consented for cMET amplification and mutation pre-screening (except for patients who are treatment-naïve potentially eligible for Sub-cohort 5a and 5b or if molecular pre-screening will be performed by NGS and local status is not available). ALK rearrangement status, if known, should also be documented in the patient's source documents prior to cMET testing, except for patients who are treatment-naïve potentially eligible for Sub-cohorts 5a, and 5b and Cohort 7. If ALK testing is not available for a patient, their ALK status will be determined centrally with a validated test along with their cMET amplification and cMET mutation status. Patients with NSCLC of pure squamous cell histology can enter pre-screening without EGFR mutation or ALK testing or result, however patients with pure squamous cell histology and are known to have EGFR mutations in exons 19 and 21 or ALK-positive rearrangement will be excluded.

Patients will be pre-screened for cMET amplification based on GCN (and ALK rearrangement status, if applicable) by FISH and for cMET mutations by RT-PCR at a Novartis-designated central laboratory following the signing of the molecular pre-screening Informed Consent Form (ICF). Next Generation Sequencing (NGS) may be used as primary pre-screening diagnostic, if assay becomes available. Patients with previously determined cMET mutation or amplification by a Novartis designated central laboratory (as detected by the same

validated NGS assay used in this protocol) who have consented for the use of those results, will be allowed to enter directly the screening phase of the INC280A2201 study. For patients coming from another Novartis study using the same central lab or being rescreened, repeat tumor biopsy or additional archival tumor may not be required provided the central laboratory confirms adequate tumor tissue remains for the required study analyses.

All patients in Cohorts 1, 2, 3, and 4 must have failed 1 or 2 prior lines of systemic therapy, while patients enrolled in Cohorts 5 and 7 must be treatment-naïve for advanced disease. Patients enrolled in Cohort 6 must have failed 1 prior line of systemic therapy for advanced/metastatic disease.

Patients with cMET mutation will be enrolled based on the prior therapy status in Cohort 4 or Sub-cohort 5b or Cohort 7, irrespective of their cMET GCN. Patients without cMET mutations, will be enrolled in Cohort 1 (Sub-cohorts 1a or 1b), Cohort 2, and Cohort 3 and Sub-cohort 5a, based on their cMET GCN and prior treatment status. Patients enrolled in Cohort 6 can be either with cMET GCN  $\geq 10$  without cMET mutations or with cMET mutation irrespective to their cMET GCN. The enrollment in this Cohort 6 will only start upon enrollment completion of the respective Sub-cohort 1a or Cohort 4.

Only the cMET amplification and mutation test results from the pre-screening analysis performed by the Novartis-designated laboratory will be used to assign patients into the following 7 cohorts:

- Cohort 1: Pre-treated patients with cMET GCN  $\geq 6$ , including:
  - Sub-cohort 1a: Patients with a cMET GCN of  $\geq 10$ , or
  - Sub-cohort 1b: Patients with a cMET GCN of  $\geq 6$  and  $< 10$ , or
- Cohort 2: Pre-treated patients with cMET GCN  $\geq 4$  and  $< 6$ , or
- Cohort 3: Pre-treated patients with cMET GCN  $< 4$ , or
- Cohort 4: Pre-treated patients with cMET mutations regardless of cMET GCN, or
- Cohort 5: Treatment-naïve patients with cMET dysregulation, including:
  - Sub-cohort 5a: Patients with a cMET GCN  $\geq 10$ , or
  - Sub-cohort 5b: Patients with cMET mutations regardless of cMET GCN, or
- Cohort 6: Pre-treated patients with either cMET GCN  $\geq 10$  without cMET mutations or cMET mutations regardless of cMET GCN or,
- Cohort 7: Treatment-naïve patients with cMET mutations regardless of cMET GCN

For the interim and final analyses in Cohort 2 (cMET GCN  $\geq 4$  and  $< 6$ ), the study targets to have at least 40% of patients with cMET GCN  $\geq 5$  and  $< 6$ . Enrollment in each cohort will be controlled via Interactive Response Technology (IRT) system.

Each cohort/sub-cohort of the study will enroll patients in parallel. Patients in all cohorts will be treated with 400 mg INC280 twice daily (BID) using the tablet formulation, administered orally on a continuous dosing schedule.

Efficacy assessment of tumor response and progression will be performed every 6 weeks (i.e., every 2 cycles) from the first day of treatment with INC280 until RECIST 1.1 disease progression as determined by investigator and confirmed by Blinded Independent Review Committee (BIRC). This schedule must be followed regardless of dose interruptions.

Confirmation of response is required for all response endpoints, as per RECIST 1.1. All radiological assessments obtained at screening/baseline, during treatment and during the follow-up phase should be performed using the same modality (method) and will be submitted to the designated independent imaging vendor for review by BIRC.

Approximately 30 enrolled patients at selected sites (regardless of cohort assignment) will have full PK samples and ECGs collected. The rest of the patients will have sparse PK samples and ECGs collected (see [Table 7-6](#) and [Table 7-7](#)). At the time of eligibility confirmation, the IRT system will inform the site about which PK and ECG schedule should be followed by the patient.

[figure not shown]
In Cohort 1 and Cohort 5, all of the efficacy analyses will be performed separately for each of the two sub-cohorts.

Interim analyses for futility will be performed separately for Sub-cohorts 1a and 1b and Cohorts 2 and 4 when there are at least 28 evaluable patients in each cohort/sub-cohort. Interim analyses for futility for Cohort 3 will be performed when there are at least 20 evaluable patients in Cohort 3. Evaluable patients are defined as those patients who have completed at least 6 cycles of treatment (18 weeks) or have discontinued the study treatment earlier. The decision to stop for futility at interim will be based on the probability of success (POS) which will be calculated based on the evaluable patients in each cohort/sub-cohort. One (or more) of the cohorts/sub-cohorts will be stopped for futility if the respective POS is less than 10% at the interim analysis. In each of Sub-cohorts 1a and 1b and Cohorts 2 and 4, if 7 or fewer responses are observed in 28 evaluable patients at interim analysis, then the respective cohort/sub-cohort will be stopped for futility. If at the time when the 28th patient is enrolled a minimum of 8 responders have not yet been observed, accrual in the cohort/sub-cohort may be temporarily suspended until either the minimum number of 8 responders is observed or results of the interim analysis allow the cohort/sub-cohort to continue. In Cohort 3, if 5 or fewer responses are observed in 20 evaluable patients at interim analysis, then this cohort will be stopped for futility. If at the time when the 20th patient is enrolled a minimum of 6 responders have not yet been observed, accrual may be temporarily suspended in the cohort until either the minimum number of 6 responders is observed or results of the interim analysis allow the cohort to continue. No interim analysis for futility is planned for Cohort 5, Cohort 6 and 7.

The primary analysis will be conducted when all treated patients in their respective cohort/sub-cohort (if not stopped for futility at interim analysis) have completed at least 6 cycles of treatment (18 weeks) or discontinued treatment earlier. Due to the expected difference in enrollment rate for each cohort/sub-cohort, the primary analysis for the different cohorts/sub-cohorts may occur at different times. The primary analysis for any cohort that was stopped for futility may be combined with the primary analyses for other cohorts.

In Cohorts 1, 2, 3 and 4, treatment with INC280 would be considered to have clinically relevant efficacy if an ORR of ~35% is observed in that cohort/sub-cohort for the corresponding primary analysis. In addition, 5 hypotheses will be tested as following for the cohorts/sub-cohorts ( $H_{i0}$  and  $H_{i1}$  correspond to cohort/sub-cohort i where i=1a, 1b, 2, 3 or 4):

$H_{i0}$ : ORR  $\leq 25\%$

In favor of the alternative

$H_{i1}$ : ORR > 25%

For Sub-cohorts 5a, 5b and Cohort 7, treatment with INC280 would be considered to have clinically relevant efficacy if an ORR of ~55% is observed in that cohort for the corresponding primary analysis. In addition, 3 hypotheses will be tested as following for the cohorts/sub-cohorts ( $H_{i0}$  and  $H_{i1}$  correspond to sub-cohort i where i=5a, 5b or 7):

$H_{i0}$ : ORR  $\leq$  35%

In favor of the alternative

$H_{i1}$ : ORR > 35%

The tests will be performed based on the exact CI for ORR in each cohort/sub-cohort using a one-sided  $\alpha= 0.025$  level.

Data from Cohort 6 will help characterize the safety and efficacy of INC280 in pre-treated Cohorts 1a and 4. Efficacy and safety data will be presented for Cohort 6 alone and also may be analyzed by combining the patients with a cMET GCN of  $\geq 10$  from Sub-cohort 1a and Cohort 6 to further evaluate the precision of the efficacy estimates. Similar analysis may be carried out for pre-treated patients with cMET mutations regardless of cMET GCN combining the patients from Cohort 4 and Cohort 6. No hypothesis testing is planned for Cohort 6.

[figure not shown]
Data from Cohort 7 will help to further characterize the safety and efficacy of INC280 in treatment-naïve group with cMET mutations regardless of cMET GCN. Efficacy and safety data will be presented for Cohort 7 alone and also in combination with the patients from Sub-cohort 5b to further evaluate the precision of the efficacy estimates. Cohort 7 efficacy data may be pooled with Sub-cohort 5b once Cohort 7 enrolment is closed and when all treated patients in Cohort 7 have completed at least 6 cycles of treatment (18 weeks) or discontinued treatment earlier.

In addition to the imaging vendor conducting the BIRC review, the study will be supported by a Central Laboratory for the routine safety assessment (i.e., hematology, chemistry, coagulation, and urinalysis), a central vendor for ECG assessments and by interactive web or voice response system (IRT) for patient registration and drug supply. For details on study assessments, refer to [Section 7](#).

Refer to [Figure 4-1](#) for an overview of the study design.

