## Amendment 4 (17-Nov-2016)

### Amendment rationale

As of 15-Nov-2016, a total of 157 patients have been enrolled in the study [19 patients in Cohort 1a (GCN $\geq$ 10); 42 patients in Cohort 1b (GCN  $\geq$  6 and  $<$  10); 54 patients in Cohort 2 (GCN  $\geq$  4 and  $<$  6); 30 patients in Cohort 3 (GCN  $<$  4); and 12 patients in Cohort 4 (cMET exon 14 skipping mutated)].

As of 30-Aug-2016, Cohort 3 has been suspended due to futility based on the planned interim analyses as outlined in the protocol. No new safety signal for INC280 has been observed.

The main purpose of this amendment is to implement a new Cohort 5 to investigate the safety and antitumor activity of INC280 in treatment-naïve patients for advanced/metastatic disease (stage IIIB or IV) NSCLC harboring cMET exon 14 skipping mutations (regardless of cMET amplification) or very high cMET gene amplification (GCN  $\geq$  10 without cMET mutations).

[figure not shown]
Increasing data confirm that cMET dysregulations such as cMET exon 14 skipping mutations and high cMET amplification are emerging as independent molecular drivers and predictors of response to cMET inhibition in NSCLC patients, irrespective of the number of prior lines of therapy including some preliminary evidence in the treatment-naïve setting ([Frampton 2015](#), [Jenkins 2015](#), [Mendenhall 2015](#), [Paik 2015](#), [Waqar 2015](#), [Liu 2015](#), [Schuler 2016](#), [Drilon 2016](#)).

Promising activity with INC280 in cMET dysregulated (either cMET amplified or cMET exon 14 skipping mutated) advanced NSCLC has been observed in the phase I study [[CINC280X2102](#)] ([Schuler 2016](#)). In patients with cMET amplified (GCN  $\geq$ 6) NSCLC, a 47% Overall Response Rate (ORR) and a median Progression Free Survival (PFS) of 7.4 months were reported.

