### **4.2 Timing of interim analyses and design adaptations**

In Cohort 1, the interim analysis will be performed separately for each of the two sub-cohorts. Interim analyses for futility assessment are planned for each cohort/sub-cohort when at least 28 patients in each of Sub-cohorts 1a and 1b, and Cohorts 2 and 4, and 20 patients in Cohort 3 have completed at least 6 cycles of treatment (18 weeks) or have discontinued treatment earlier. The decision to stop for futility at interim will be based on the probability of success (POS) and will be calculated based on the actual number of evaluable patients at the interim analysis. A cohort/sub-cohort will be stopped for futility if the respective POS is less than 10% at the interim analysis. With 28 evaluable patients for interim analysis in each of the Sub-cohorts 1a and 1b, and Cohorts 2 and 4, if 7 or fewer responses are observed, then the cohort/sub-cohort will be stopped for futility. If at the time that the 28th patient is enrolled a minimum of 8 responders have not yet been observed, accrual in the cohort/sub-cohort may be temporarily suspended until either the minimum number of 8 responders are observed or results of the interim analysis allow the cohort/sub-cohort to continue.

With 20 evaluable patients for interim analysis in Cohort 3, if 5 or fewer responses are observed then the respective cohort will be stopped for futility. If at the time that the 20th patient is enrolled a minimum of 6 responders have not yet been observed, accrual in the cohort may be temporarily suspended until either the minimum number of 6 responders are observed or results of the interim analysis allow the cohort to continue.

No interim analysis for futility assessment is planned for Cohort 5, Cohort 6 and Cohort 7.

All evaluable patients at the time of the data cut-off for the interim analysis will be used to obtain the futility boundary using the POS criteria. The futility boundary will be calculated according to the actual number of evaluable patients in the interim analysis.

The statistical considerations for the interim analysis can be found in [Section 10.7](#).

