#### 10.7 Interim analysis

In Cohort 1, the interim analysis will be performed separately for each of the two sub-cohorts. Interim analyses for each cohort/sub-cohort are planned when at least 28 patients in each of Sub-cohorts 1a and 1b, Cohorts 2 and 4, and 20 patients in Cohort 3 have completed at least 6 cycles of treatment (18 weeks) or have discontinued treatment earlier. For the interim analysis and the final analysis in Cohort 2 (cMET GCN  $\geq 4$  and  $< 6$ ), the study targets to have at least 40% of patients with cMET GCN  $\geq 5$  and  $< 6$ .

No interim analysis for futility is planned for Sub-cohorts 5a and 5b, Cohort 6 and Cohort 7.

The decision to stop for futility for the respective cohort/sub-cohort at interim will be based on the probability of success (POS). POS is the probability of a positive conclusion of the

study if the study continued beyond interim, (i.e., till the final analysis), given the interim observed data (x) and success among n patients. Thus,

$$POS = \text{Prob}[\text{ Final observed ORR} \geq 35\% \mid x, n]$$

Minimally informative Beta distribution prior ([Neuenschwander et al 2008](#)) with prior mean equal to 25% will be used, i.e., the prior distribution will be Beta (0.3333, 1) for the POS calculations at the interim analysis.

The respective cohort will be stopped for futility at the interim analysis if the respective POS < 10%. The interim analysis will be performed by cohort in which the patients are enrolled. In addition, for Sub-cohort 1a and 1b, Cohorts 2 and 3, sensitivity analysis on the primary endpoint may be performed at interim analysis excluding patients with cMET mutations.

All evaluable patients at the time of the data cut-off for the interim analysis will be used to obtain the futility boundary using the POS criteria. The futility boundary will be calculated according to the actual number of evaluable patients in the interim analysis.

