**Table 10-7      Operating Characteristics for Sub-cohort 1a, Sub-cohort 1b, Cohort 2 and Cohort 4**

True ORR (%)	Probability of a cohort to stop at IA* (%)	Probability for positive conclusion in final analysis for a cohort (%)	Probability for negative conclusion in final analysis for a cohort (i.e. not stop at IA* and success criterion not met at final analysis) (%)
10	99.50	0.00	0.50

True ORR (%)	Probability of a cohort to stop at IA* (%)	Probability for positive conclusion in final analysis for a cohort (%)	Probability for negative conclusion in final analysis for a cohort (i.e. not stop at IA* and success criterion not met at final analysis) (%)
20	81.82	0.12	18.06
25	59.97	2.34	37.68
30	36.48	15.01	48.51
35	18.21	44.00	37.79
40	7.40	75.38	17.22
45	2.42	93.11	4.47
50	0.63	98.73	0.64

\*Assuming interim analysis at 28 evaluable patients

### Cohort 3

The operating characteristics at this sample size have > 60% probability of stopping the trial for futility when the true ORR is < 25%. With 69 patients and 20 evaluable patients for interim analysis, when the true ORR is 10% then the probability of stopping for futility at the interim analysis is > 90%. If the true ORR is 20%, the probability of stopping for futility at the interim analysis is > 80% and the probability of positive conclusion at the final analysis is < 1%.

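### The interim evaluability rule fills the futility set by outcome, so the stated stop probabilities are too low if accrual runs past the 28th (Cohort 3: 20th) patient

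*Protocol*

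**What the plan says.** The definition in Protocol 4.1 reads: "Evaluable patients are defined as those patients who have completed at least 6 cycles of treatment (18 weeks) or have discontinued the study treatment earlier". Sections 4.2 and 10.7 and SAP 2.11 use the same trigger.

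A cohort "will be stopped for futility if the respective POS is less than 10% at the interim analysis". In Sub-cohorts 1a and 1b and Cohorts 2 and 4 this means stopping "if 7 or fewer responses are observed in 28 evaluable patients at interim analysis"; in Cohort 3, "if 5 or fewer responses are observed in 20 evaluable patients at interim analysis". Protocol 10.7 takes every patient evaluable at the data cut-off, and 4.2 adds: "The futility boundary will be calculated according to the actual number of evaluable patients in the interim analysis". No section limits the set to the first 28 (20) treated or requires 18 weeks since first dose.

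If 8 responders (6 in Cohort 3) have not been seen when the 28th (20th) patient is enrolled, accrual may be suspended. The pause is optional.

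Table 10-7 carries one condition: "Assuming interim analysis at 28 evaluable patients". It says nothing about how those 28 come to be evaluable.

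**The concern.** Entry to the interim set depends on outcome. Scans are every 6 weeks and a response must be confirmed, so a confirmed response usually cannot exist before about week 12. A patient who progresses and stops at week 6 is counted at week 6. A responder enrolled on the same day is counted at week 18. While new patients keep arriving, the set over-represents failures. Recalculating the boundary for the actual number evaluable (Table 10-3) corrects for how many patients are in the set, not for which ones.

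At stake is power. An active cohort could be closed more often than the tables say. SAP section 2, which holds these tables, is written to be carried into section 9.7 of the CSR.

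**Working it through.** **1. Reproduce the stated figures.** Treat the interim patients as unselected, with X ~ Binomial(n, p).

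- n = 28, stop if X ≤ 7: P = 59.97%, 18.21% and 2.42% at p = 25%, 35% and 45%. All match Table 10-7.
- n = 20, stop if X ≤ 5: P = 24.54% at p = 35%. This matches Table 10-8.
- Boundary: "the prior distribution will be Beta (0.3333, 1) for the POS calculations at the interim analysis". The predictive probability of at least 25 responders in 69 is 0.0543 at 7/28, 0.1398 at 8/28 and 0.0999 at 5/20, as printed.
- Positive conclusion at p = 35%: the sum over x ≥ 8 of P(X = x) · P(Binomial(41, p) ≥ 25 − x) = 44.00%, as printed.

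The tables are therefore correct for an unselected set and make no allowance for selection.

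**2. Inputs the documents only partly supply.**

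- *Accrual.* No planned rate is given. The first patient was treated on 16-Jul-2015 (Amendment 2). By 15-Nov-2016, about 70 weeks later, Amendment 4 counts "54 patients in Cohort 2": 54/70 = 0.77 per week. The whole study had 148 patients on 20-Jul-2016 (Amendment 3) and 157 on 15-Nov-2016, so at most 9 of the 54 came in that last stretch. At least 45 came in the first 53 weeks: 45/53 = 0.85 per week. I used 0.5 to 1 per week.
- *Early stopping.* No rate is given. As a proxy, Protocol 1.2.1.2.2 reports a median PFS of 3.55 months and an ORR of 20% in an earlier study. Week 18 is 126/30.4375 = 4.14 months. If PFS is exponential, 1 − 2^(−4.14/3.55) ≈ 55% have progressed by then. If nearly all are non-responders, that is 0.55/0.80 ≈ 69% of them. I used 40% to 80%.

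**3. Simulate the rule as written.** Accrual is Poisson. Non-responders stop at an exponential time. Among responders, 5% stop before week 18 and none before week 12. The look is held when the 28th (20th) patient becomes evaluable.

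| Case (true ORR) | Stated P(stop) | Simulated P(stop) |
|---|---|---|
| 28 patients, no pause, 0.5–1/week (25%) | 59.97% | about 66–84% |
| 28 patients, no pause, 0.5–1/week (35%) | 18.21% | about 22–47% |
| 28 patients, no pause, 0.5–1/week (45%) | 2.42% | about 3–13% |
| 20 patients (Cohort 3), no pause, 0.5/week (35%) | 24.54% | 30.4–40.5% |
| 28 patients, pause applied, 60% off early, 0.25–2/week (35%) | 18.21% | 19.2–22.0% |
| 20 patients, pause applied, 60% off early, 0.25–2/week (35%) | 24.54% | 25.9–28.9% |
| First 28 by enrolment order (35%) | 18.21% | 18.7% |

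In the second row the mean interim ORR falls from 35% to between 33.6% and 27.9%. The probability of a positive conclusion runs from 44.4% (no real change) down to 36.0%, against 44.00% stated.

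**4. Check the stopping model.** An exponential time lets some patients stop before their first scan. Placing stops mostly after the week-6 and week-12 scans, with 60% to 85% of non-responders off by week 18, gives 26–28%, 29–35% and 34–42% at 0.5, 0.75 and 1 patient per week for ORR 35%. These lie inside the range in the table.

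**The case against.** The strongest reply is that the protocol already contains the remedy. With the pause applied, the stop probability at ORR 35% is within about 1 to 4 points of the stated value. That stands, and it means the bias is not automatic. But the pause is optional, and final enrolment was 54 in Cohort 2 and 30 in Cohort 3, past their triggers of 28 and 20. Sub-cohort 1b reached 42, which is weaker evidence because it was split out of Cohort 1 only in Amendment 3.

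Second, a reader might infer from those counts that Sub-cohort 1b or Cohorts 2 or 3 were closed wrongly. The documents do not support this. They give neither the interim cut-offs nor the numbers evaluable. Accrual had also nearly stopped: with at most 9 patients added across all cohorts in the 17 weeks to mid-November 2016, at least 33 of the 42 in 1b and 45 of the 54 in Cohort 2 were already enrolled by 20-Jul-2016. The rule uses everyone evaluable at cut-off, so selection shrinks as the set approaches the whole cohort.

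Third, much larger figures are possible on paper: at 2 patients per week without a pause, the stop probability at ORR 35% reaches 78.4%. Nothing in the documents supports that pace for a single cohort. At 0.25 per week the excess is only about 2 to 6 points.

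Fourth, the interims are finished, none is planned for Cohorts 5 to 7, and SAP 2.1 reports primary analyses of 1b, 2 and 3 at the 15-Apr-2019 cut-off. This stands. It limits the remedy mainly to how the tables are described.

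**Conclusion.** The point holds conditionally. If accrual continues past the trigger, the rule biases interim ORR downward and Tables 10-7 and 10-8 understate the probability of a futility stop. At ORR 35% the understatement is about 4 to 29 points (22 − 18 to 47 − 18). This rests on assumed accrual of 0.5 to 1 per week, 40% to 80% of non-responders off drug before week 18, no pause, and a look held at the 28th evaluable patient. With the pause it is small.

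The direction is firm, but the size in this trial cannot be fixed from the documents. The bias only favours stopping: it costs power and does not raise false positives. It does not affect the primary analysis, which waits until all treated patients have completed 18 weeks or stopped.

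**What to change.** In Protocol 4.1, 4.2 and 10.7 and SAP 2.11, define the interim set as patients whose first dose was at least 18 weeks before the cut-off (or the first 28, Cohort 3: 20, treated), whether or not they stopped early. This costs one sentence in each place and, for any future look, a slightly later date.

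Because the interims are done, the practical step is in reporting. State in the SAP and CSR that Tables 10-7 and 10-8 (SAP 2-6 and 2-7) hold only for such a set, or replace them with simulated values that include accrual and discontinuation. The first option is a footnote; the second is a short simulation with its assumptions stated.

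Re-tabulating the 1b, 2 and 3 interim counts on the redefined set is optional. It would show how far selection mattered in practice, but would change no decision.
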